4.5 Duration of Study Participation

The study will be open for 4 years after beginning enrollment.

4.6 Total Number of Participants and Sites

Recruitment will end when approximately 400 participants are enrolled. It is expected that approximately 400 participants will be enrolled in order to produce 300-350 evaluable participants. There were 350 procedures done on patients matching the inclusion and exclusion criteria in the last year. Based on the simplicity of the intervention and historical enrollment for patients undergoing orthopedic surgery, we anticipate at least 25% participation.

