Physical therapy records with regards to ambulation distance and exercise endurance will be examined. Daily assessments of pain via VAS will be obtained by the nursing staff as per standard protocol. APS-POQ form will be given on POD1.

After discharge subjects will receive a 7-10 day prescription for acetaminophen 1000mg every 8 hours, meloxicam 15mg oral once daily, and tramadol 50mg oral, every 4-6 hours, PRN (12 tablets to be dispensed). Subjects will call the provider to request refills as needed.

CONFIDENTIAL

This material is the property of the NYU School of Medicine and Langone Medical Center. Do not disclose or use except as authorized in writing by the study sponsor

Interventional Template Version: 28 APR 2017

[figure not shown]
After discharge the research staff will call the subjects up to every other day for the first week, twice in the second week, once weekly for the third and 4th weeks and then monthly after discharge to ascertain pain level, reported narcotic usage, and functional status. Research staff will verify documented narcotic refills through epic and pharmacy records. Four to eight weeks after injury subjects will complete a SMFA as well as another APS-POQ form over the phone with a trained interviewer.

	Pre-op	Post-op: Inpatient	Post-op: Discharge
Standing	Acetaminophen 1gm, oral (every 6-8 hours, not to exceed 4gm daily, review liver function prior to administration)	Acetaminophen 1gm, oral (every 6-8 hours, not to exceed 4gm daily, review liver function prior to administration)	Acetaminophen 1gm, oral (every 6-8 hours, not to exceed 4gm daily, review liver function prior to administration)
	Meloxicam 15mg oral, once daily	Ketorolac 30mg inj, once daily in AM, starting POD1 (15mg>65 years of age and/or renal impairment) Pregabalin (Lyrica) 50mg, oral every 8 hours (hold for sedation)	Meloxicam 15mg oral, once daily
Mild		Ice Therapy PRN (alternating 15 min on/off for skin evaluation)	
Moderate		Tramadol 50mg oral, every 8 hours, PRN	
Severe		Tramadol 100mg, oral, every 8 hours, PRN	
Breakthrough		Oxycodone 5mg, oral every 6 hours, PRN	Tramadol 50mg oral, every 4-6 hours, PRN (12 tablets to be dispensed)

CONFIDENTIAL

This material is the property of the NYU School of Medicine and Langone Medical Center. Do not disclose or use except as authorized in writing by the study sponsor
Interventional Template Version: 28 APR 2017

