6.1 General Approach

As treated Sample. The primary analyses will follow the as-treated principle in order to evaluate the true outcome of the intervention as experienced by the patient who is blinded to the intervention.

Missing Data. It is anticipated that the data for some subjects will be incomplete for various reasons: missed clinic visits, refusal to answer a sensitive question on a questionnaire, onset of illness, loss-to-follow-up, etc. All occurrences of incomplete data will be investigated to carefully document the reasons for the missing data.

Sensitivity Analyses. To evaluate the robustness of the main results to reasonable perturbations of the methods and assumptions used, competing statistical methods (those not used in the main analyses) will be relegated to serving as a guide to our confidence in the main results.

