6.2 Analysis of Endpoints

Primary Endpoints:

amount (mg) of narcotics (oral morphine mg equivalents) used
duration of narcotic use
patient reported pain scores

Secondary Endpoints:

length of stay
progress with physical therapy: distance ambulated, range of motion, exercises done
reported long-term narcotic use at home/SAR
discharge location: home, acute rehab, skilled nursing facility
documented narcotic refills
falls
adverse events

The analysis of narcotic Use, VAS, APS-POQ, and SMFA scores will rely on a univariate repeated-measures analysis of variance model for mean score. This model is in the class of models commonly known as a unirep-ANOVA models. It assumes that the mean score is a function of elapsed time and the treatment regimen assigned. This model takes into account the fact that the subject's repeated measures are correlated. The fitted model will provide statistical estimates of the mean levels, the treatment-effect differences between mean levels, the standard deviation, the intra-class correlation coefficient, 95% CIs, standard errors (SE), and statistical hypothesis tests. The estimates of means will be used to compute summary criteria such as area under the curve (AUC) for each regimen. All estimates reported will be presented their 95% CIs.

CONFIDENTIAL

This material is the property of the NYU School of Medicine and Langone Medical Center. Do not disclose or use except as authorized in writing by the study sponsor

Interventional Template Version: 28 APR 2017

All endpoints will be evaluated as fits the data set with graphical figures such as scatter plots, box-and-whisker plots, and frequency histograms to visualize the distribution of these outcomes and their relationships to covariates and treatment assignment. When appropriate descriptive graphical and tabular methods, and Kaplan-Meier curves will also be estimated and presented in a graphical figure.

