6.3 Sample Size

In order to have a sufficient N to power the study a minimum of 200 subjects per anesthesia group will be recruited ($\alpha=0.05$, $\beta=0.2$). If the difference in the morphine equivalent consumption, is found to be 15mg daily with a standard deviation between the groups of 25mg, we will need 90 subjects per group in order to reject the null hypothesis with the probability (power) 0.8. The Type I error probability associated with this test of this null hypothesis is 0.05. To allow for within group analyses and accommodate for the poor follow-up rate in fracture patients we will need 400 patients.

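### The plan expects 50–100 of 400 patients to be non-evaluable, but neither defines evaluable nor says how incomplete series enter its repeated-measures ANOVA

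*Combined protocol and SAP*

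**What the plan says.** Section 4.6 sets the expected loss: "It is expected that approximately 400 participants will be enrolled in order to produce 300-350 evaluable participants". Section 6.3 gives two reasons for the total: "To allow for within group analyses and accommodate for the poor follow-up rate in fracture patients we will need 400 patients".

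On missing data, section 6.1 foresees incomplete records, loss to follow-up included, and then commits to one action: "All occurrences of incomplete data will be investigated to carefully document the reasons for the missing data". The sensitivity analyses in the same section name no method and are not tied to missing data. Section 8 adds only that blanks on the case report form must be explained.

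On the model, section 6.2 says that the analysis of narcotic use, VAS, APS-POQ and SMFA "will rely on a univariate repeated-measures analysis of variance model for mean score". It adds that correlation between repeated measures is taken into account and that an intra-class correlation will be estimated. It does not say what happens to a patient with a missing occasion.

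On the schedule, section 3.1 has nurses record VAS every four hours in hospital. The telephone schedule once patients have gone home reads: "call the subjects up to every other day for the first week, twice in the second week, once weekly for the third and 4th weeks". Monthly calls follow. The Protocol Summary puts participation at 3 months.

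**The concern.** No section says what makes a patient evaluable, although section 4.8 allows the study to stop if data are not evaluable enough. Nor does any section say how a missed call, a loss to follow-up, a withdrawal or a death enters the analysis of narcotic amount or pain. The named model does not settle this. Univariate repeated-measures ANOVA, as usually run, takes one row per patient with every occasion filled and excludes the rest.

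The schedule does not produce such rows. In-hospital series end on different days, and the first-week calls have a maximum but no fixed number. An analyst would have to choose a set of occasions and then lose every patient with a gap in it, including that patient's first post-operative days. Section 2.4 expects the greatest benefit in the first day or two, when scores come from routine charting.

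Two things are at stake. One is precision, because collected data would go unused. The other is comparability of the arms: if staying in follow-up is related to pain or narcotic use after randomisation, the patients left in the analysis are a selected group. Two analysts could also follow the present text faithfully and report different primary results.

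**Working it through.** **1. The plan's own loss (section 4.6).** 400 − 350 = 50, and 50/400 = 12.5%. 400 − 300 = 100, and 100/400 = 25%.

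**2. Is it a power problem?** Section 6.3 assumes a difference that "is found to be 15mg daily with a standard deviation between the groups of 25mg" and concludes that "we will need 90 subjects per group in order to reject the null hypothesis with the probability (power) 0.8". With two-sided α = 0.05 (sidedness is not stated), n per arm = 2 × (1.960 + 0.842)² × (25/15)² = 43.6, so 44; the t-based figure is 44.6, so 45. Two arms of 45 make 90, so the stated figure reproduces if group means a two-arm anesthesia cohort. With 300–350 evaluable, a cohort has 75–87.5 per arm. Power is Φ(0.6 × √(n/2) − 1.96): 95.7% at 75 and 97.8% at 87.5. For the 10 mg threshold in the Protocol Summary, 0.6 becomes 0.4 and within-cohort power is 68.8–75.4%, against 80.7% with all 100 per arm. With the cohorts pooled it is 93.4–96.3%. Power for 15 mg therefore survives the planned loss, and the issue is mainly how the data are used.

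**3. How many patients would have complete series?** My count of calls from section 3.1 is 3–4 in week 1 and 2 in week 2 (5–6 in total), plus 1 each in weeks 3 and 4 and 2 monthly calls (9–10 in total). Aim 2 (section 2.2) measures narcotic use for 2 weeks after surgery, so at most the 5–6 calls apply to it. Pain may run to 3 months. Suppose that evaluable means every call completed and that calls are independent; the documents state neither. The complete share is then p^m.

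| Response per call, p | m = 5–6 (narcotics, 2 weeks) | m = 9–10 (pain, 3 months) |
|---|---|---|
| 95% | 0.95⁵ = 77%, 0.95⁶ = 74% | 0.95⁹ = 63%, 0.95¹⁰ = 60% |
| 90% | 0.90⁵ = 59%, 0.90⁶ = 53% | 0.90⁹ = 39%, 0.90¹⁰ = 35% |

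To reach the plan's 75–87.5%, response per call would have to be 94.4–97.8% over 5–6 calls (0.75^(1/5) to 0.875^(1/6)), or 96.9–98.7% over 9–10 calls (0.75^(1/9) to 0.875^(1/10)).

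**4. What could a completer analysis do?** This is illustrative, and every input is assumed: 200 per arm, six occasions, SD 20, intra-class correlation 0.5, and arm differences of 15, 15, 10, 8, 5 and 2 mg/day (mean 55/6 = 9.17). From the third occasion, the logit of dropout is an intercept plus 0.9 times the standardised previous score.

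- Main run, intercept −2.7: completers are 71% of control and 79% of SSI patients. The estimate is 8.44, a shortfall of 0.73 (8%). The SE is 1.67 against 1.52 with full data, a ratio of 1.10. A random-intercept mixed model on all observed scores gives 9.10.
- Independent repeat, intercept −2.7: 67% and 76% complete. The estimate is 8.25, a shortfall of 0.92 (10%). The SE is 1.82 against 1.60, a ratio of 1.14. All observed scores give 9.17.
- Independent repeat, intercept −3.0: 74% and 81% complete. The estimate is 8.33, a shortfall of 0.84 (9%). The SE is 1.63 against 1.51, a ratio of 1.08. All observed scores give 9.14.

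**5. Is the direction fixed?** No. A second illustration used 10 contacts, SD 25, intra-class correlation 0.5, about 20% dropout and a true effect of 15 mg/day. Completer estimates are set against the full-data value of the same run:

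- dropout unrelated to use: 14.98 against 15.06
- related in both arms: 14.21 against 14.91
- related in control only: 12.69 against 14.92
- related in SSI only: 16.59 against 15.01

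The effect can be understated, overstated or unchanged.

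**The case against.** The strongest objection is that the plan never says incomplete patients will be dropped. A compound-symmetry model with an intra-class correlation, as section 6.2 describes, can be fitted by likelihood to all available data. This stands. A reader might infer that the primary analyses are completer analyses and hence biased, but the text supports only that handling is unspecified and that the usual form of the named model excludes patients with gaps. Indeed, with no common set of occasions, a literal completer set could not be formed until someone chose the occasions.

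Further points stand in part:

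- A reader might suppose that all 50–100 non-evaluable patients were lost after discharge and have in-hospital scores. The documents do not say so. Section 4.7 allows withdrawal at any time and termination for a newly met exclusion. The exclusions in section 4.2 include nerve block and intra- or post-operative ketamine, which can arise after consent. Some patients may have no post-operative score.
- Applying 9–10 calls to narcotics would overstate the attrition, because Aim 2 stops at 2 weeks and section 6.2 makes long-term use at home a secondary endpoint.
- The simulated bias is under half of its own SE in the main run (0.73 against 1.67) and uses SD 20 where section 6.3 has 25. Its dropout is missing at random by construction, which favours the mixed model. Section 6.1 links none of its reasons for missing data to pain or narcotic use.
- The plan has some protection. In-hospital VAS is collected by nurses, refills are checked in records, and section 6.2 allows Kaplan-Meier curves, which could handle censoring of narcotic duration. The t-tests and rank tests in the Protocol Summary do not need complete series. None of these says how a gap enters the model that section 6.2 assigns to narcotic use and pain.

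**Conclusion.** The concern holds in a limited form. The plan expects 12.5–25% of patients to be non-evaluable, leaves the term undefined, gives no rule for incomplete series, and names a model whose usual form does not fit its own schedule. Run that way, the model would discard early in-hospital scores.

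The certain cost of that choice is lost precision. Selection bias is a risk that depends on whether loss is related to pain or narcotic use, and its size and direction cannot be derived from the documents. Under the assumed dropout the illustration gives 0.7–0.9 mg/day off a 9.2 mg/day effect and an SE about 8–14% wider. That is small beside the plan's 10 mg and 15 mg figures. At 95% response per call, complete series would be about 74–77% for narcotics and 60–63% for pain, if evaluable meant every call and calls were independent.

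This should be changed before analysis; it does not undermine the sample size for the 15 mg effect. Whether patients are grouped as treated or as assigned is a separate question.

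**What to change.** - **Section 6.2:** replace the univariate repeated-measures ANOVA with a likelihood-based mixed model by post-operative day. It should use all observed scores from every randomised patient with at least one post-operative score.
- **Section 4.6:** define those patients as evaluable, and report by arm the number with no post-operative score.
- **Section 6.1:** state that scores up to death or withdrawal are used, and report deaths by arm.
- **Section 6.1, sensitivity analyses:** add one analysis of departures from missing-at-random. Control-based imputation of missing post-discharge scores is one example; other forms would also serve.

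The cost is SAP wording and a little more analysis work, with no new patients or data. The main model relies on missing-at-random, which the data cannot verify; the sensitivity analysis shows how far the result depends on it.

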4.7 Participant Withdrawal or Termination

Participants are free to withdraw from participation in the study at any time upon request. An investigator may terminate participation in the study if:

- Any clinical adverse event (AE), laboratory abnormality, or other medical condition or situation occurs such that continued participation in the study would not be in the best interest of the participant
- The participant meets an exclusion criterion (either newly developed or not previously recognized) that precludes further study participation

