SAE	Serious adverse event
IV	Intravenous
PO	Taken orally
PRN	Taken as needed
TID	Taken three times per day
Q4h	Taken every four hours
CI	Confidence interval
SD	Standard deviation; a parameter which characterizes a population distribution
SE	Standard error
SSI	Surgical Site Injection
ANOVA	analysis of variance; a linear model
NSAID	Non-steroidal anti-inflammatory drug
LOS	Length of Stay

CONFIDENTIAL

This material is the property of the NYU School of Medicine and Langone Medical Center. Do not disclose or use except as authorized in writing by the study sponsor
Interventional Template Version: 28 APR 2017

Protocol Summary

Title	Effects of a Surgical Site Injection on Pain Scores and Narcotic Use after Orthopedic Trauma Surgery
Short Title	Understanding and Improving post-operative Pain in the Fracture Population
Brief Summary	This is a phase I, randomized, single-blind, placebo-controlled, single-center study of the effects of surgical site injection on pain and narcotic utilization in participants who undergo surgery for lower extremity fractures. 400 participants with lower extremity fractures who are admitted for operative fixation will be included in the study. Participants will be randomized to receive either a pain cocktail injection around the fracture site and surrounding tissues or control (no injection). An analysis of pain scores, rehabilitation progress, length of stay, narcotic utilization, and satisfaction scores will be performed.
Phase	Clinical study phase 1
Objectives	To understand the effect of surgical site injections of post-operative pain control
Methodology	phase I, randomized, single-blind, placebo-controlled, single-center study
Endpoint	10mg change in narcotic utilization daily or 15mm change in VAS
Study Duration	4 years
Participant Duration	3 months
Duration of IP administration	Once during surgery
Population	400 participants with peritrochanteric fractures
Study Sites	NYU Langone (Kimmel, Tisch, Langone Orthopedic Hospital, Lutheran)
Number of participants	400
Description of Study Agent/Procedure	Peri-incisional injection of 40cc 0.25% bupivacaine, 5 mg morphine sulfate (1 mg/cc, 5 cc total), and 30 mg of ketorolac (30 mg/cc, 1 cc total) into soft tissue and musculature surrounding the fracture site and 0.25% Marcaine 10 mL into the subcutaneous tissue surrounding the surgical incision.
Reference Therapy	Reference is a control
Key Procedures	Surgical Site injection

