2.2 Specific Aims

AIM 1: To determine if SSI given to during lower extremity fracture surgery reduces post-operative pain. This will be evaluated through the randomizing patients who either receive general or spinal anesthesia into two separate groups, injection or control, and monitoring their pain scores afterwards both in the hospital and outpatient settings. (The type of anesthesia will be determined by the treating anesthesiologist; it is not an experimental variable.)

AIM 2: To determine if SSI given during lower extremity fracture surgery significantly changes post-operative narcotic usage. Using the same groups as above, this will be evaluated through the measurement of narcotic usage both in the immediate post-operative period and for 2 weeks after surgery.

AIM 3: To determine if SSI given during lower extremity fracture surgery alters post-operative function, length of stay, and complications after surgery. This will be measured through rehabilitation documentation, discharge documentation, chart review, and patient interviews.

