3.1 Description of Study Design

The researchers will use NYU admission records, emergency room records, orthopedic consult records, and immediate care records to identify patients eligible for participation in the study. Orthopedic residents and authorized researchers will consent and enroll patients pre-operatively.

Subjects with a qualifying fracture will be randomized to either the SSI or control group. Subjects in the SSI group will receive a peri-incisional injection of 40cc 0.25% bupivacaine (marcaine), 5 mg morphine sulfate (duramorph) (1 mg/cc, 5 cc total), and 30 mg of ketorolac (30 mg/cc, 1 cc total) into soft-tissue and musculature surrounding the fracture site and 0.25% Bupivacaine (Marcaine) 10 mL into the subcutaneous tissue surrounding the surgical incision. The control group will receive no injection. The injection will be administered by the subjects NYU orthopedic surgeon, all of whom are familiar with the technique. The patient will be blinded to if a medication is being injected. Subjects will not receive ketorolac if they have kidney disease or a history of allergy to NSAIDS or aspirin. The dose of ketorolac will be reduced to 15 mg (30 mg/cc, 0.5cc total) in subjects older than 65 years of age, in subjects with a history of peptic ulcer disease, a CrCl of 30 to 50 ml/min, or subjects with diabetes. These modifications are recommended by the manufacturer and are used in standard practice. A sub group analysis will be done on patients who receive this lower dosage to see if it has an impact on the data.

After initial recruitment, subjects' pain will be assessed via visual analog scale (VAS) by nursing staff on a q4h basis. A standardized regimen of pain medication will be given to all subjects who are enrolled. Pre-operatively subjects will receive acetaminophen 1gm oral (every 6-8 hours, not to exceed 4gm daily) and meloxicam 15mg oral once daily. Post-operatively, subjects will receive acetaminophen 1gm oral (every 6-8 hours, not to exceed 4gm daily), ketorolac 30mg injection, once daily in AM, starting POD 1(15mg for patients >65 years of age and/or renal impairment), and pregabalin (Lyrica) 50mg oral every 8 hours (held for sedation). Ice PRN for mild pain, tramadol 50mg oral every 8 hours PRN for moderate pain, and tramadol 100mg oral every 8 hours PRN for severe pain. Oxycodone 5mg oral every 6 hours PRN will be given for breakthrough pain.

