4.2 Exclusion Criteria

An individual who meets any of the following criteria will be excluded from participation in this study:

1. Pregnant women
2. Treatment with Arthroplasty
3. Patients who receive a peripheral nerve block
4. Patients who receive intra-op or post-op ketamine
5. Patients with concomitant TBI or MR
6. Polytrauma patients
7. Pathologic Fractures
8. Patients with a contraindication to any of the medications on the study list due to other medical problems such as renal or liver disease or due to allergy/intolerance
9. Patients with prior extremity weakness resulting from stroke or other neurological condition
10. Prior or current history of narcotic use
11. Patients with advanced dementia
12. NYUMC Students, Residents, Faculty

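### Section 4.7 lets the investigator end a patient's participation after a single intra-operative injection, and the plan does not say that outcome follow-up continues

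*Combined protocol and SAP*

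**What the plan says.** Section 4.7 gives the investigator two discretionary grounds for ending participation. The first is an adverse event, laboratory abnormality or other medical situation that "occurs such that continued participation in the study would not be in the best interest of the participant". The second reads "The participant meets an exclusion criterion (either newly developed or not previously recognized) that precludes further study participation". One of the exclusions in section 4.2 is "Patients who receive intra-op or post-op ketamine". Its post-operative part can only be met after the injection has been given or withheld.

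The Protocol Summary gives the duration of study drug administration as "Once during surgery". What continues afterwards is a shared analgesic regimen and data collection. Section 3.1 already lets staff hold pregabalin for sedation and lower the ketorolac dose.

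On outcomes, Aim 2 in section 2.2 relies on "measurement of narcotic usage both in the immediate post-operative period and for 2 weeks after surgery". Section 3.1 sets a schedule of telephone calls after discharge for pain, narcotic use and function. It adds "Research staff will verify documented narcotic refills through epic and pharmacy records" and "Four to eight weeks after injury subjects will complete a SMFA as well as another APS-POQ form". None of these provisions mentions a patient whose participation has been ended. Section 6.1 requires reasons for missing data to be documented and names no method for handling them.

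**The concern.** After surgery there is no study injection left to stop. A problem with a regimen drug can be met by holding or changing that drug, and a telephone call rarely adds risk. Section 4.7 nevertheless speaks only of ending participation in the study. It does not separate stopping a drug from stopping follow-up.

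Patients removed this way are selected by something that happened, or was noticed, after randomization. Post-operative ketamine is the clearest case: it is an analgesic, so its use may reflect pain, which is a primary outcome. The decision is discretionary, the trial is single-blind for the patient, and section 6.4 tells the surgical team the allocation. Nothing says that whoever ends participation is masked.

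At stake are parts of the primary endpoints in section 6.2 (narcotic use after discharge, its duration, and later pain scores), the only SMFA and the second APS-POQ. Reported pain and questionnaire answers that were never collected cannot be recovered at analysis.

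**Working it through.** The plan gives no figure for terminations, so there is none to reproduce. Section 4.6 expects 300 to 350 evaluable of 400, a shortfall of 50/400 = 12.5% to 100/400 = 25%, but does not say how much of it would come from section 4.7.

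**Step 1. What stops and what does not.**
- Needs the patient, so ends with participation on a plain reading: calls, SMFA, second APS-POQ.
- Could still be read from records, though the plan does not say it will be: refills, length of stay, discharge location.
- Already in hand: VAS and inpatient narcotic use recorded before termination.
- Still covered by section 7.3: unresolved adverse events, and later events reasonably related to the study.

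**Step 2. Calls.** Section 3.1 allows up to every other day in week 1 (0 to 4 calls), 2 in week 2, 1 each in weeks 3 and 4, then monthly. Taking the 3-month participant duration in the Protocol Summary as the end (assumption), months 2 and 3 add 2.
- Minimum 0 + 2 + 2 + 2 = 6; maximum 4 + 2 + 2 + 2 = 10.
- Termination before discharge loses all 6 to 10.
- Termination at about day 30 loses the 2 monthly calls: 2/10 = 20% to 2/6 = 33%. If discharge came some days after surgery and the week-4 call is still pending, 3 are lost: 3/10 = 30% to 3/6 = 50%.

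**Step 3. Questionnaires.** Four to eight weeks is day 28 to day 56 after injury. Termination before day 28 loses the SMFA and the second APS-POQ. Termination between day 28 and day 56 loses them only if they are not yet done.

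**Step 4. Aim 2's two-week narcotic window.** Share lost = (14 − day of termination)/14.
- Day 2: 12/14 = 86%.
- Day 7: 7/14 = 50%.
- Day 14 or later: none.

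**Step 5. Illustrative bias (assumed inputs).** Suppose a share q of one arm is terminated and would later have used D mg/day more than the patients retained. The retained mean is then too low by q × D. Take D = 25 mg/day, one planning SD from section 6.3, and q = 1% to 5% of a 200-patient arm (100 from each anesthesia cohort), that is, 2 to 10 patients.
- Shift: 0.01 × 25 = 0.25 to 0.05 × 25 = 1.25 mg/day.
- Against the 10 mg/day endpoint in the Protocol Summary: 0.25/10 = 2.5% to 1.25/10 = 12.5%.
- Against the 15 mg/day planning difference in section 6.3: 0.25/15 = 1.7% to 1.25/15 = 8.3%.
- With D measured from the whole arm's mean, the shift is qD/(1 − q): at 5%, 1.25/0.95 = 1.3 mg/day, practically the same.
- If both arms lose similar patients in similar numbers, the between-arm bias is about zero.

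**Step 6. Is D = 25 reasonable?** The discharge supply in section 3.1 is 12 tramadol tablets of 50 mg, or 600 mg. Attachment 14.1 equates 40 mg tramadol with 10 mg oral morphine, so this is 600 × 10/40 = 150 mg. Over 7 to 10 days that is 150/10 = 15 to 150/7 = 21 mg/day. An excess of 25 mg/day is more than the whole first prescription and would need refills. D = 25 is therefore a generous choice.

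**The case against.** The best reply is that the trigger is narrow. Section 4.7 is permissive. It applies only when continuing is against the patient's interest or an exclusion precludes it, and once the injection is given an event would seldom make calls harmful. An investigator who reads it sensibly would change a drug and keep calling. Section 2.4 expects the greatest benefit in the first day or two, and those data are mostly in hand before termination. Refills sit in records. The consent pages are not available for this review and may address data after termination.

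Much of this stands. It is why the point is minor, and why no rate of loss can be claimed. It does not close the gap. The available text leaves continued collection to individual judgement, by people who may know the arm, and records cannot supply reported pain, SMFA or APS-POQ.

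Three stronger readings are tempting and are not supported:
- **Safety follow-up ends too.** Section 7.3 follows unresolved events and covers related later ones. Only routine recording of other new events is tied to the individual's last day of participation.
- **Day-30 termination loses most of follow-up.** In calendar days, (90 − 30)/90 = 67% remains ahead. But calls are front-loaded, so the loss in contacts is the 20% to 33% in Step 2, plus questionnaires not yet done.
- **The primary comparison is biased.** The documents show neither how many patients would be terminated nor any difference by arm.

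**Conclusion.** The concern holds as a minor design point about outcome data. Section 4.7 as written permits selective loss after randomization, and nothing in the available documents requires collection to continue. For a terminated patient the loss runs from all 6 to 10 calls and both later questionnaires (termination before discharge) to about 2 calls (at about day 30, questionnaires done). For the trial, the number affected is unknown and the likely bias is small: 0.25 to 1.25 mg/day in one arm under a generous illustration, and about zero if the arms are alike. This rests on ending participation meaning the end of patient contact, on follow-up closing at 3 months, and on the assumed shares and excess use in Step 5. The reason to act is that the data cannot be recovered later and the remedy uses contacts already planned.

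**What to change.** Reword section 4.7 so that an adverse event, laboratory abnormality, medical condition or exclusion criterion first met or first recognized after randomization leads to stopping or changing the regimen drug concerned, not to ending follow-up. Calls, chart and refill review, APS-POQ and SMFA then continue to 3 months, and the patient stays in the primary analysis. Allow two exceptions: the participant withdraws consent, or the investigator documents that contact itself is not in the participant's best interest. In either case record-based collection continues as far as consent permits.

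State in section 4.2 that ketamine given during or after surgery to a randomized patient is recorded as a protocol deviation or rescue analgesia and is not a reason to drop the patient. Without this, the data could be collected and then left out.

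The cost is a wording amendment with IRB approval and continued contact with a few patients. In the illustration this is 2 × 6 = 12 to 10 × 10 = 100 calls, all already in the schedule. Tying the adverse-event window in section 7.3 to the planned 3-month date is optional and not needed for this point.
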